11.7. Screening, Recruitment and Consent

The research team will be required to obtain patient consent and carry out data management. The data required for the study will be collected as part of patients' standard care.

Screening and recruitment will take place in clinics in the Dermatology Department at the Royal Victoria Infirmary.

11.8. Identification and screening of participants

Participants will be identified from all of the psoriasis clinics including the phototherapy department.

11.9. Recruitment procedures

Recruitment to be undertaken from biologics clinic, PUVA clinic, Psoriasis and drug monitoring clinics and phototherapy department.

11.10. Consent procedures

Face to face consent following participant assessment of patient information.

11.11. Data handling and record keeping

All investigators and study site staff will comply with the requirements of the current Data Protection Act with regards to the collection, storage, processing and disclosure of personal information and will uphold the Act's core principles. All medical records will be kept in accordance with Trust policy.

11.12. Statistical Analysis plan

The statistical aspects of this research has been reviewed by an individual with relevant statistical expertise:

[name], Institute of Health & Society, Newcastle University, [name] , [name],
[contact]

Descriptive statistics will be used to describe the prevalence of all data recorded.

We will investigate the relationship between LSM and potential risk factors.

11.13. Analysis Methods

All of the data will be assembled in a spreadsheet that will be designed and checked by our statistical collaborators.

The analysis will be performed including all patients and then the group will be divided based on the PASI score (PASI >10 and PASI <10) and analysis of the separate groups will be performed.

We will calculate the prevalence of liver fibrosis (the proportion of the population affected by liver fibrosis) by dividing the number of participants with liver fibrosis in the study population by the total number of people in study population.

For the analyses we will perform these 3 times using the 3 different cut off values for liver stiffness measurements of 7Kpa, 7.9Kpa and 9.5Kpa. There is currently no consensus as to which value is most appropriate. We will therefore analyse using all three.

Regression analyses will be carried out, the results of which will be used to inform a power calculation for future research.

- Logistic regression will be used to consider the association between liver fibrosis (yes/no) and methotrexate dose (continuous).
- Linear regression will be used to consider level of liver fibrosis (continuous i.e. independent of cut offs) and methotrexate dose (continuous).
- Regression models will also be used to investigate the relationship between other risk factors (e.g. BMI, waist circumference, alcohol consumption etc.) and liver fibrosis.

Analysis will be carried out in STATA 15.

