Number of study sites	One (the Newcastle upon Tyne Hospitals NHS Foundation Trust)
Study population size	250
Study duration	2 years

7. Introduction

Patients with psoriasis appear to have higher rates of liver fibrosis in comparison to the general population. The higher rates of risk factors for liver fibrosis such as obesity, alcohol and diabetes are important; however there have been concerns that methotrexate can contribute to liver fibrosis. Ever since methotrexate has been used to treat psoriasis there have been concerns over the risk to liver health. Until the 1990s liver biopsies were recommended pre and during MTX therapy. Despite the increasing importance of biologic therapies, methotrexate remains the most commonly used systemic agent in the UK. The majority of patients needing systemic therapy will try methotrexate first as per NICE guidance.

This study aims to investigate the prevalence of liver fibrosis in a group of patients with psoriasis by measuring liver stiffness measurement (LSM) using Transient Elastography (TE), now increasingly used for monitoring of liver fibrosis. The previous standard to monitor liver fibrosis was liver biopsy but concerns over morbidity and mortality along with sampling error have led to a decline in this test being performed. In addition to measuring liver stiffness, the cumulative methotrexate dose and other important factors including BMI, waist circumference and alcohol intake will be recorded. A univariate analysis will be performed to investigate the relationship between all measured risk factors and LSM.

The ultimate goal is to use the prevalence data to perform a power calculation to determine the number of participants required to conduct a study to determine which factors can predict the risk of liver fibrosis. Increasingly experts believe that other risk factors for liver fibrosis such as obesity and alcohol intake may be more important than methotrexate. We want to determine whether or not methotrexate is an independent risk factor for liver fibrosis in patients with psoriasis and if so whether we can predict which populations are most at risk from negative side effects of methotrexate. Using this data a risk prediction model can be built to allow optimal and safe prescribing of methotrexate.

8. Background

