The first line systemic therapy for psoriasis is methotrexate. Ciclosporin, acitretin and biologic agents are alternatives if methotrexate is not appropriate or successful. Methotrexate is an antineoplastic antimetabolite with anti-inflammatory and immunosuppressant properties. The exact mechanism of action remains unclear and it is likely that different dosing regimens have different biological effects. The low dose weekly regimen used for psoriasis treatment may work by increasing the level of anti-inflammatory proteins called adenosines or by an effect on cell division due to inhibition of the tetrahydrofolate reductase enzyme. At higher doses, used in chemotherapy regimens, methotrexate works by causing significant inhibition of tetrahydrofolate dehydrogenase and prevents the formation

of tetrahydrofolate, which is necessary for the formation of thymidylate an essential component of DNA. Methotrexate is used in many conditions including psoriasis, psoriatic arthritis, rheumatoid arthritis and Crohn's disease. In chronic plaque psoriasis 50-60% of patients treated with methotrexate see a reduction in PASI score of 75% in 3-6 months¹⁰.

Since the early days of methotrexate treatment for psoriasis there have been concerns regarding liver toxicity. However, a number of confounding factors have always made it unclear whether or not the methotrexate was responsible for the liver fibrosis identified in some patients.

Due to the concerns regarding liver fibrosis and methotrexate the early guidelines recommended pre-treatment liver biopsy and then repeat liver biopsy for every 1.5g cumulative methotrexate. As the use of methotrexate became more widespread the enthusiasm for routine liver biopsies decreased. Data also emerged showing that the development of significant liver fibrosis was highly unlikely with less than 5g cumulative methotrexate⁸.

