Fibrotic livers have reduced elasticity due to the deposition of fibrous tissue in the hepatic parenchyma. TE gives a 'liver stiffness measurement' (LSM) using pulsed-echo ultrasound as a surrogate marker of fibrosis. The LSM correlates well with the degree of hepatic fibrosis in a range of liver diseases, including NAFLD, hepatitis B, hepatitis C and in patients treated with methotrexate²². In a study of 246 patients with biopsy-proven NAFLD, TE achieved high AUROCs for the detection of \geq stage 2 fibrosis, \geq stage 3 fibrosis and cirrhosis (0.84, 0.93 and 0.95, respectively) and performed better than a number of simple non-invasive scores in the staging of fibrosis. In that study, TE had a high NPV of 96% for \geq stage 3 fibrosis at a cut-off of 7.9 kPa but only modest PPV (52% at 7.9 kPa and 72% at 9.6 kPa)²³. A low LSM reliably excludes advanced fibrosis, but the optimum cut-offs for clinical use are yet to be determined. Previous observational studies looking at the prevalence of liver fibrosis and advanced liver fibrosis used LSM >7 kPa and LSM >9.5 kPa as their cut-off values³⁻⁵. However, there are significant limitations to using TE. Results may be invalid in those with central obesity (BMI >35 kg/m²) or type 2 diabetes²⁴. For obese patients, the Fibroscan XL probe has been developed that is associated with fewer LSM failures (1.1% vs16%) than the M probe and was accurate for the diagnosis of \geq F2 fibrosis and cirrhosis (AUROC 0.83 and 0.94, respectively)²⁵. However, even with the XL probe, 10% of patients with a BMI >28 kg/m² have a difference of ≥ 2 fibrosis stages between TE and liver biopsy²⁶.

Despite its limitations, the usefulness of TE in detecting liver fibrosis in patients with psoriasis has been demonstrated and TE is increasingly recommended to be used in monitoring patients taking methotrexate ^{4, 21}.

9. Objectives

Primary objective To determine the prevalence of liver fibrosis in patients with psoriasis (LSM >7.9kPa, >7.0 kPa, > 9.5kPa) and to evaluate the relationship between the cumulative dose of methotrexate and liver fibrosis in patients with psoriasis.

Secondary objectives

1. To evaluate the relationship between other liver fibrosis risk factors and non-invasive markers of liver fibrosis in patients with psoriasis using univariate analysis.

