2. To perform a power calculation to determine number of participants required for a large multivariable analysis to investigate factors influencing liver fibrosis and determine which risk factors are most important in the development of live fibrosis.

Primary outcome To determine the prevalence of liver fibrosis in patients with psoriasis (LSM >7.9kPa, >7.0 kPa, > 9.5kPa) and to evaluate the relationship between the cumulative dose of Methotrexate and liver fibrosis in patients with psoriasis.

10. Method and Study Design

The study will be a cross sectional design. Patients with psoriasis with a PASI score of at least 5 and duration of at least 1 year will be invited to join the study.

All of the data that we are interested in is recorded as part of standard clinical care and we do not want to repeat measurements unnecessarily. We will therefore accept values for blood tests that have been recorded within 6 months of patient recruitment and LSM values that have been recorded within 12 months of recruitment to the study.

For patient severity scores and assessments of clinical data such as BMI, these will be collected at the time of recruitment.

The following data will be recorded for each patient:

- Patient demographics: Age, Gender, Ethnicity Socioeconomic status.
- Disease severity: Duration of psoriasis, Age of onset of psoriasis), Year of diagnosis (best approximation), Year first seen by a dermatologist, PASI at recruitment, Worse ever PASI, DLQI at recruitment, worse ever DLQI, Family history of psoriasis (first degree relative such as parent, sibling or child).
- Characteristics: Height and Weight, Body Mass Index (BMI), Waist circumference, smoking status, alcohol intake questionnaire and AUDIT score, Blood pressure , skin type and skin cancer risk factors.
- Liver stiffness measurements: Value, >7.9kPa (yes/no), > 7kPa (yes/no), > 9.5kPa (yes/no).
- Alcohol related questions: AUDIT score, Average alcohol intake in the last year (units per day or units per week)*, A history of sustained excessive alcohol consumption of > 35 units/week for females or > 50units per week for males for more than 1 year, A history of excessive alcohol consumption (>14 units/day for both) – document the average units/day or week and the duration of alcohol, A history of alcohol dependence.
- Comorbidities –has the patient ever had or required treatment for the following illnesses and year of onset of illness:

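### No adjusted methotrexate estimate is planned, so a crude dose effect would feed a multivariable power calculation and could misstate its N in either direction

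*Protocol*

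**What the plan says.** The methotrexate part of the primary objective (sections 6 and 9) is "to evaluate the relationship between the cumulative dose of methotrexate and liver fibrosis in patients with psoriasis". Section 11.13 gives two models for it:

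- binary outcome: "Logistic regression will be used to consider the association between liver fibrosis (yes/no) and methotrexate dose (continuous";
- continuous outcome: "Linear regression will be used to consider level of liver fibrosis (continuous i.e. independent of cut offs) and methotrexate dose (continuous".

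Other factors come in a separate item: "Regression models will also be used to investigate the relationship between other risk factors (e.g. BMI, waist circumference, alcohol consumption etc.) and liver fibrosis". Section 11.13 does not itself use the word univariate, but section 7 (Introduction) does: "A univariate analysis will be performed to investigate the relationship between all measured risk factors and LSM". Cumulative methotrexate dose is among the measured items in that paragraph. Secondary objective 1 also limits the other risk factors to univariate analysis. The only split of the sample in 11.13 is by PASI above or below 10, which does not adjust for metabolic or alcohol-related risk.

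Four other statements bear on this choice:

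- Section 7: "We want to determine whether or not methotrexate is an independent risk factor for liver fibrosis in patients with psoriasis".
- Section 8 (Background), on the earlier evidence: "a number of confounding factors have always made it unclear whether or not the methotrexate was responsible".
- Section 9, secondary objective 2: "To perform a power calculation to determine number of participants required for a large multivariable analysis". Section 11.13 adds that the regression results will inform a power calculation for future research.
- Section 10 and the case report form collect age, sex, BMI, waist, diabetes, HbA1c, alcohol intake, AUDIT score and psoriasis duration.

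**The concern.** The protocol names the weakness of earlier work, collects the variables that could reduce it, and then specifies models that leave them out. Two things follow.

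First, a dose-only slope mixes any methotrexate effect with the effects of obesity, diabetes, alcohol and age, to the extent that these go with dose. The bias can run either way. Heavier or longer-treated patients may accumulate more dose, or patients with liver risk may be given less.

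Second, the slope is meant to be used. A sample size for one factor in a multivariable model needs the adjusted effect of that factor and the share of its variance explained by the other covariates (R-squared). The planned models give neither. If the crude effect goes in as it stands, the follow-on study is sized for the wrong effect.

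**Working it through.** **The plan's own figure.** Section 11.6 gives 250 patients (up to 500) as a pilot number, without alpha, power, effect size or precision target. There is nothing to reproduce.

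**Inputs.** From the documents: N = 250; prevalence 11% at LSM >7 kPa, 8.1% and 14.1% at >9.5 kPa (section 8, from three different studies). Assumed, because the documents give no values: two-sided alpha 0.05, power 80%, true adjusted odds ratio (OR) 1.3 per SD of dose, one confounder with OR 2.0 per SD, correlation rho between dose and confounder of ±0.2 to ±0.3.

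**Step 1: crude effect.** Approximation: ln OR(crude) = ln OR(adjusted) + rho × ln OR(confounder), with ln 1.3 = 0.262 and ln 2.0 = 0.693.

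**Step 2: sample size.** N = (1.960 + 0.842)² / [p(1-p)(ln OR)²], divided by (1 - R²) for a multivariable model. With one confounder, R² = rho². At p = 0.11 the constant is 7.849 / 0.0979 = 80.2.

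| rho | ln OR(crude) | OR(crude) | N from crude effect | N needed, adjusted |
|---|---|---|---|---|
| +0.3 | 0.470 | 1.60 | 363 | 1,280 |
| +0.2 | 0.401 | 1.49 | 499 | 1,214 |
| -0.2 | 0.124 | 1.13 | 5,237 | 1,214 |
| -0.3 | 0.054 | 1.06 | 27,072 | 1,280 |

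The last column is 1,165 (the N for OR 1.3 with R² = 0) divided by 0.91 or 0.96. Most of the error comes from the effect, not from R²: at rho = +0.3 the effect alone accounts for 1,165 / 363 = 3.2-fold and R² for 1 / 0.91 = 1.10-fold. A study of 363 patients would then have z = 0.262 × √(363 × 0.0979 × 0.91) - 1.960 = 1.49 - 1.96 = -0.47, a power of about 32% instead of 80%.

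**Step 3: R² alone.** The factor 1 / (1 - R²) is 1.11, 1.25 and 1.43 for R² of 0.1, 0.2 and 0.3, so N rises by 11% to 43% even if the effect is right.

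**Step 4: no true methotrexate effect.** With confounder OR 1.5 to 2.5 and rho from -0.3 to +0.3, the crude OR runs from exp(-0.3 × ln 2.5) = 0.76 to exp(0.3 × ln 2.5) = 1.32.

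**Step 5: is adjustment feasible at N = 250?** For the linear model, the detectable partial correlation is tanh(2.802 / √247) = 0.176 with dose alone and tanh(2.802 / √241) = 0.179 with dose plus six covariates. The degrees of freedom cost almost nothing. For the logistic model, the expected events are 250 × 0.081 = 20, 250 × 0.11 = 27.5 or 250 × 0.141 = 35. These mix cut-offs and populations, so they are only a guide. Within one sample the lower cut-offs cannot have fewer events than 9.5 kPa, and enlarging to 500 would double the counts. With six parameters they still give only 3.4 to 5.9 events per parameter at 250.

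**The case against.** The strongest reply is that this is a pilot, and that the adjusted question belongs to the later study. Much of that stands.

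- A reader might infer that the study fails its own primary objective. The documents do not support this. The objective asks only for the relationship, and a crude association answers that. The sentence on an independent risk factor stands in the Introduction, in a paragraph that opens with sizing a later study and ends with a future prediction model. Secondary objective 2 leaves the ranking of risk factors to that later analysis. The Introduction is loosely worded, but independence is not a listed objective.
- A reader might also infer that the study cannot supply the inputs for the power calculation. That is too strong. It supplies prevalence, the distribution of dose and crude effects. R-squared can be computed from the collected data, and the protocol fixes no formula that would rule it out.
- The direction of confounding is not known. Section 8 says that alternatives are used when methotrexate is unsuitable or unsuccessful, but does not tie this to liver risk.
- Covariate details often sit in a statistical analysis plan, which is not shown here. However, the protocol does not merely leave the model open: section 7 calls the analysis univariate and 11.13 names dose alone.

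What remains is that 11.13 sends the regression results into a multivariable sample size, and the only methotrexate effect it plans is crude. The pilot label does not answer this, because that calculation is one of the pilot's stated products.

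**Conclusion.** The point holds in limited form and should be fixed. No adjusted methotrexate estimate is planned, although the protocol recognises confounding and collects the main confounders. The crude estimate cannot speak to independence. As the effect input to secondary objective 2, it could make N about 3.5 times too small (363 against 1,280 at rho = +0.3) or about 4.3 times too large (5,237 against 1,214 at rho = -0.2). These sizes rest on assumed odds ratios and correlations and on a log-odds approximation. They show what plausible confounding could do, not what it will do. The prevalence objective is untouched, and the remedy can be applied at analysis.

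**What to change.** In 11.13, add a prespecified multivariable linear regression of continuous LSM (log-transformed if skewed) on cumulative methotrexate dose. Use a short list of covariates already collected: age, sex, BMI or waist, diabetes, alcohol (AUDIT or units per week) and psoriasis duration. Report it beside the crude estimate. Keep any adjusted logistic model sparse, in line with the events observed at each cut-off.

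For secondary objective 2, use the adjusted coefficient with its confidence interval and the observed R-squared of dose on the covariates. State in 11.13 that the crude estimates do not address independence, and align the Introduction with that.

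The cost is protocol wording and a few lines of code, with no new data. The interval for methotrexate may widen: by √1.11 = 1.05 to √1.43 = 1.20 for R-squared of 0.1 to 0.3, before any gain from covariates that explain LSM. A few patients with missing covariates would drop out of the adjusted model.

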Cardiac disease (Heart failure, Cardiac arrhythmias, Stroke , Coronary artery disorders, Angina , Myocardial infarction), Vascular diseases (Hypertension, Peripheral vascular disorders, Deep vein thrombosis, Pulmonary embolism , Disorders of metabolism and nutrition (Diabetes mellitus, Impaired glucose tolerance , Dyslipidaemia , Endocrine diseases (Thyroid disease), Nervous system disorders(Demyelinating diseases ,Epilepsy) , Respiratory, thoracic and mediastinal disorders (Asthma, COPD) , Renal and urinary tract diseases (Chronic renal failure), Hepatobiliary diseases (Viral hepatitis infection, Other liver disease), Gastrointestinal diseases (Peptic ulcer), Gastrointestinal inflammatory conditions (Crohn’s disease, Ulcerative colitis), Psychiatric diseases (Depression, Anxiety), Infections and infestations (Tuberculosis). Immune system disorders, Skin and soft tissue disorders (Psoriatic arthritis (Diagnosis of PSA by a rheumatologist? And Year of diagnosis), Other types of cancers: Skin cancers (Non-melanoma skin cancer, Squamous cell, carcinoma, Basal cell carcinoma) Melanoma skin cancers and pre-

cancerous skin lesions (Melanoma skin cancer, Melanoma in situ, Bowen disease, Actinic keratosis, Keratoacanthoma)

- Duration on methotrexate in months, cumulative dose of methotrexate
- UV Therapy– (yes/No), duration and type, response
- Any current systemic drug, Oral PUVA or biologics for psoriasis, Small molecule immunomodulator therapy for psoriasis (Apremilast or dimethyl fumarate) – dose, frequency and date started
- All previous systemic or biologics or oral PUVA, small molecule immunomodulator therapy for psoriasis – start and stop dates and stop reason
- Any other systemic drug or biologic drugs (dose and frequency) and durations with start dates and stop dates and duration
- Current medications and start dates – including pimecrolimus or tacrolimus
- Folic acid: Duration and Frequency
- Blood tests: HBA1C, Fasting glucose (if available), Lipid profile including, Triglycerides, HDL cholesterol, AST, ALT, Abnormal AST in the past year, Abnormal ALT in the past year, Worse ever AST/ALT, Platelets, Procollagen three peptide (PIIINP), Albumin.
- Previous liver ultrasound report, Previous liver biopsy report

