11.6. Sampling strategy

Total sample size: 250 (can be increased to up to 500).

As this is a pilot study, this should be an adequate sample to test recruitment and the estimate effect sizes to include in a formal statistical power calculation for a planned larger study.

We are interested to recruit a mix of patients receiving different types of treatment including phototherapy and biologics. We will aim to recruit at least 100 patients who are receiving or have previously received methotrexate.

We will compare our study population to BADBIR population to ensure we demonstrate that our sample is representative.

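### The methotrexate dose models treat never-users as a neutral zero-dose reference, yet some may have been refused methotrexate because of their liver, and no item records why it was never started

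*Protocol*

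**What the plan says.** Half of the primary objective (section 9) is the relationship between cumulative methotrexate dose and liver fibrosis. Section 11.13 gives two models. For the cut-offs: "Logistic regression will be used to consider the association between liver fibrosis (yes/no) and methotrexate dose (continuous". For stiffness itself: "Linear regression will be used to consider level of liver fibrosis (continuous i.e. independent of cut offs) and methotrexate dose (continuous". The analysis set is stated as "The analysis will be performed including all patients", followed by a split on PASI. There is no separate term for never-users and no restriction to users.

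Section 11.6 sets the numbers: "Total sample size: 250 (can be increased to up to 500" and "We will aim to recruit at least 100 patients who are receiving or have previously received methotrexate". It also seeks a mix of treatments, naming phototherapy and biologics. The exclusions in section 11.5.2 are pregnancy and language difficulty; liver disease is not among them.

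On how patients come to have no methotrexate, section 8 says: "Ciclosporin, acitretin and biologic agents are alternatives if methotrexate is not appropriate or successful". On past practice, section 7 says: "Until the 1990s liver biopsies were recommended pre and during MTX therapy".

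For methotrexate itself, section 10 lists duration and cumulative dose. For previous systemic drugs it adds "start and stop dates and stop reason", which can apply only to a drug that was started. The medications table in the case report form has cumulative dose and duration for methotrexate and no reason field of any kind.

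**The concern.** In a model with one continuous dose term, patients at 0 g fix the lower end of the line. That is sound only if they differ from users in dose and not in the liver they had before treatment was chosen. If a liver finding was the reason for withholding methotrexate, that patient's fibrosis is counted at zero dose, and the treated group is depleted of the same kind of patient. Both effects lower the slope.

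Section 7 wants to learn whether methotrexate is an independent risk factor and to support safe prescribing. Section 11.13 uses the regression results to plan the next study. An estimate pulled down would give false reassurance and would feed too small an effect into that power calculation.

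**Working it through.** The protocol gives no figure to reproduce for this point: 250 is justified as a pilot size, without an effect size or precision. The check therefore illustrates a bias using expected counts.

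**Inputs from the protocol**
- N = 250 and at least 100 ever-users (section 11.6), so at most 250 − 100 = 150 never-users, or 60%.
- Fibrosis prevalence p from section 8: 8.1% (>9.5 kPa), 11% (>7 kPa), 14.1% (>9.5 kPa, severe psoriasis).

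**Assumptions not in the protocol**
- Methotrexate has no true effect.
- A share c of would-be users with fibrosis is diverted to other treatment: 10%, 25% or 50%.
- Never-users are coded 0 g.

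**Ever versus never**
- Would-be users w = 100/(1 − pc); with fibrosis pw; diverted c·pw.
- Ever-users with fibrosis: pw(1 − c) of 100.
- Never-users with fibrosis: 250p − pw(1 − c) of 150.

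At p = 11%, c = 25%: w = 100/(1 − 0.0275) = 102.83; with fibrosis 11.31; diverted 2.83; ever-users 8.48 of 100; never-users 27.5 − 8.48 = 19.02 of 150. Odds ratio = (8.48/91.52)/(19.02/130.98) = 0.64.

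All shares at p = 11%:

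| c | Diverted | Ever-users with fibrosis (of 100) | Never-users with fibrosis (of 150) | Odds ratio | After removing the diverted |
|---|---|---|---|---|---|
| 10% | 1.11 | 10.01 | 17.49 | 0.84 | 0.90 |
| 25% | 2.83 | 8.48 | 19.02 | 0.64 | 0.75 |
| 50% | 5.82 | 5.82 | 21.68 | 0.37 | 0.50 |

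The odds ratios are almost the same at 8.1% and 14.1% (0.36 at 14.1%, c = 50%).

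**Why removal is only partial.** Once the diverted patients are dropped, the remaining never-users have odds p/(1 − p). Ever-users have odds p(1 − c)/(1 − p). The ratio is 1 − c at any prevalence, because the users are still depleted of fibrosis.

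**The planned model, per gram.** With doses in users assumed to be spread over 0.5 to 8 g, the all-patient logistic fit gives a null drug an odds ratio per gram of about 0.97, 0.93 and 0.83 to 0.84 at c = 10%, 25% and 50% (the range reflects how doses are spread). A true harm of 1.10 per gram appears as about 1.07, 1.02 to 1.03 and 0.93 to 0.94. Fitted in ever-users only, the model returns the true value (1.00 or 1.10) at every c, provided dose among users is unrelated to their earlier liver state.

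**Price of the restriction.** Take no diversion, p = 11% and doses evenly spaced from 0.5 to 8 g (mean 4.25, variance 4.78). The standard error of the log odds ratio per gram is 1/√[p(1 − p) × sum of squares of dose].
- Ever-users: 1/√(0.0979 × 100 × 4.78) = 0.146.
- All patients (mean dose 1.7): sum of squares = 100 × (4.78 + 2.55²) + 150 × 1.7² ≈ 1,562, so 1/√(0.0979 × 1,562) = 0.081.

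The ever-user interval is about 0.146/0.081 = 1.8 times as wide on the log scale.

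**The case against.** **Diversion is inferred.** Section 8 names no liver reason, and its list of alternatives does not include phototherapy. Pre-treatment biopsy is described as past practice. A reader might infer that the protocol shows liver patients being steered into the zero-dose group; it does not. It shows that the route is open and unrecorded.

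**The 60% is a ceiling.** Section 7 says most patients needing systemic therapy try methotrexate first, so many biologic patients will be ever-users. Coding never-users at 0 g is also an inference from the analysis set and the continuous term. Both points stand.

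**Net direction is not settled.** Section 8 raises severe psoriatic inflammation as a possible cause of liver damage. If methotrexate users have the more severe disease (an assumption), that confounding pushes upwards. The downward pull described here is one component, not a proven net result.

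**The numbers are small and this is a pilot.** At 11% prevalence the three shares mean about 1, 3 and 6 diverted patients. Approximate 95% intervals for the odds ratio at the first two are 0.37 to 1.92 and 0.27 to 1.50, both including 1. Section 11.13 speaks of association, and ranking the risk factors is left to a larger study. This limits the severity but does not make zero dose a clean reference.

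**Much can be repaired later.** A reader might infer that the bias is beyond correction because the reason is missing. That is wrong: an ever-user model needs only dose. Viral hepatitis and other liver disease with year of onset, liver ultrasound, biopsy and alcohol history are also recorded. An analysis plan not shown here could use them. It could not supply the prescribing reason, since no item shown collects it. The form ends by naming a baseline questionnaire whose content is not shown.

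**Conclusion.** The point holds as a design weakness in half of the primary objective. The all-patient dose models rest on a zero-dose group that may include patients kept off methotrexate because of their liver, and nothing in section 10 or the case report form identifies them. If such avoidance occurs, it pulls the association towards null or protective. The size depends wholly on an unknown diverted share: ever versus never odds ratios of 0.84, 0.64 and 0.37 under a null drug at 10%, 25% and 50%, with 150 never-users as the maximum.

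A reader might also infer that comparing results with and without never-users withheld for liver reasons would settle the matter. It would not. Even with perfectly recorded reasons the second analysis gives 0.90, 0.75 and 0.50, so the two could agree on a falsely protective direction. Agreement between them is no safeguard.

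**What to change.** - **Section 11.13:** fit each logistic and linear dose model in ever-users only as well, and report it beside the all-patient model. This removes the never-start bias with data already collected.
- **Case report form:** add one item for never-users: methotrexate considered but not given, and the reason, with liver-related and unknown among the options. Report never-users by reason.
- **Supporting sensitivity analysis:** use the recorded prior liver disease, ultrasound and biopsy.
- **Reporting:** present the analyses together, with no rule that makes a conclusion depend on their agreement, and describe the result as an association.

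The cost is one form field and a repeat of each dose model. The ever-user fit rests on as few as 100 patients, with intervals roughly 1.8 times as wide under the dose spread assumed above. It does not remove bias from stopping early because of the liver, which shortens cumulative dose; section 10 lists a stop reason, but the form has no field for it. Some reasons for never starting will remain unknown.
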